8.2 Study Setting and Data Sources

This study will be conducted using routinely collected data from 3 databases in 3 European countries. All databases were previously mapped to the OMOP CDM.

1. Clinical Practice Research Datalink (CPRD GOLD), United Kingdom
2. Integrated Primary Care Information Project (IPCI), The Netherlands
3. Sistema d'Informació per al Desenvolupament de la Investigació en Atenció Primària (SIDIAP), Spain

Detailed information on data sources is described in [Table 8.2.1](#).

Database selection

The selection of databases for this study was performed based on data reliability and relevance for the proposed research question among those databases onboarded and available within DARWIN EU. The selected databases fulfil the criteria required for the availability of key information on exposures (i.e. complete recording of vaccines including date and brand), outcomes (except for hospitalization), and covariates, while covering different settings and regions of Europe.

Records on SARS-CoV-2 infection and vaccination will be available in all databases. We have previously published studies showing that these databases can generate reliable evidence on COVID-19 research¹⁻⁷⁻¹⁰. Specifically, the availability of COVID-19 tests results, and linked vaccination records through national/regional immunization program (CPRD, SIDIAP) increased the reliability of the identified study exposures. Information on hospitalization will be available in SIDIAP and IPCI, which provides primary care records with (linked) hospitalization information.

No SARS-CoV-2 variant information from sequencing is available in any of the databases. We will therefore use calendar period with predominance of variants as a proxy for SARS-COV-2 variants in this study.

Information on vaccine products (i.e. monovalent/bivalent booster) are not reliably recorded in the databases, but only the vaccine brand. We will therefore use the number of vaccine doses in combination with vaccine brand for this study.

Potential for future study repetition

This study could be replicated in the future to include additional databases provided those are onboarded for DARWIN EU and fulfill the selection criteria as outlined above.

	Phase II C3-002 – Study Protocol	
	Author(s): [name], [name], [name]	Version: v2
	Dissemination level: Public	

Table 8.2.1. Description of the selected data sources.

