Country	Name of Database	Justification for Inclusion	Health Care setting	Type of Data (EHR, claims, registries)	Number of active subjects	Feasibility count of outcome/exposure (if relevant)	Data lock for the last update	Contributing to objectives
United Kingdom	CPRD GOLD	Complete records on SARS-CoV-2 infection, Covid-19 vaccination, and outcome events of interest (excl. hospitalization for COVID-19)	Primary care	EHR	3M	Covid-19: 360,198 Comirnaty: 2,822,947 Spikevax: 311,069	01/2023	1-2 for outcome “COVID-19 related death” only, 4-6
The Netherlands	IPCI	Complete records on SARS-CoV-2 infection, Covid-19 vaccination, and outcome events of interest	Primary care	EHR	1.39M	Covid-19: 941,329 Comirnaty: 1,173,104 Spikevax: 463,315	12/2022	1-6
Spain	SIDIAP	Complete records on SARS-CoV-2 infection, Covid-19 vaccination, and outcome events of interest; Include inpatient admission information.	Primary care + linkage to hospital data	EHR	5.8M	Covid-19: 3,865,976 Comirnaty: 6,548,545 Spikevax: 3,371,395	06/2022	1-6

	Phase II C3-002 – Study Protocol	
	Author(s): [name], [name], [name]	Version: v2
		Dissemination level: Public

Clinical Practice Research Datalink GOLD, United Kingdom (University of Oxford)

The Clinical Practice Research Datalink (CPRD) is a governmental, not-for-profit research service, jointly funded by the National Institute for Health and Care Research and the Medicines and Healthcare products Regulatory Agency, a part of the Department of Health, United Kingdom (UK) (<https://cprd.com>). CPRD GOLD¹¹ comprises computerized records of all clinical and referral events in primary care in addition to comprehensive demographic information and medication prescription data in a sample of UK patients (predominantly from Scotland (52% of practices) and Wales (28% of practices). The prescription records include information on the type of product, date of prescription, strength, dosage, quantity, and route of administration. Data from contributing practices are collected and processed into research databases. Quality checks on patient and practice level are applied during the initial processing. Data are available for 20 million patients, including 3.2 million currently registered patients. Approval for this study was granted via the Research Data Governance Process.

Integrated Primary Care Information Project (IPCI), The Netherlands (Erasmus)

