8.3 Study Period

The study period will start on 01/01/2021 for all databases covering the period where “any variant” was dominant. The end of the study period will be the last available date of data collection for each contributing dataset.

For analyses conducted specifically at the time of predominance of “XBB variant or later dominant” variant, the study period would start on the 01/03/2023, when XBB became the dominant variant. However, this

	Phase II C3-002 – Study Protocol	
	Author(s): [name], [name], [name]	Version: v2.1
		Dissemination level: Public

period is not covered by the data cuts currently onboarded for DARWIN EU®. Analyses will therefore start at the time when vaccine booster programs offering the 4th vaccine dose were rolled out in each country.

Table 8.3.1. illustrates the periods of COVID-19 variant dominance across UK, The Netherlands and Spain.

Table 8.3.1. Periods of variant dominance

	UK	The Netherlands	Spain
Any variant	01/2021 - ongoing	01/2021 – ongoing	01/2021 - ongoing
Alpha and earlier variants	01/01/2021 - 01/06/2021	01/01/2021 – 01/07/2021	01/01/2021 – 01/07/2021
Delta	01/06/2021 – 15/12/2021	01/07/2021– 15/12/2021	01/07/2021– 15/12/2021
Omicron	15/12/2021 – 01/03/2023	15/12/2021 – 01/03/2023	15/12/2021 – 01/03/2023
XBB variant or later dominant	01/03/2023 - ongoing	01/03/2023 - ongoing	01/03/2023 - ongoing

<https://ourworldindata.org/grapher/covid-variants-bar?time=latest&facet=none&country=GBR~ESP~FIN~NOR~NLD>, accessed 15/08/2023

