8.6 Variables

8.6.1. Exposures

Vaccination against SARS-CoV-2

COVID-19 vaccine exposure status will be defined by number of received doses, i.e. 1 dose only, completed primary vaccination course (2 doses), 3rd dose (1st booster) and 4th dose (2nd booster). For booster doses, we will distinguish between monovalent or adapted/bivalent vaccines where possible. Where such detailed information is not available in the databases, we will use the number of vaccine doses received and the vaccine brand.

Start of the respective studies will depend on when the respective vaccines became available. An overview of dates of marketing approval is provided in [Table 8.6.1.1](#) below.

Table 8.6.1.1 Marketing approval dates

Country	UK	The Netherlands	Spain
Responsible Agency	MHRA	EMA	
Comirnaty original strain (monovalent)	08/12/2020	21/12/2020 ¹⁴	
Comirnaty original strain + omicron ba1 (adapted, bivalent)	02/09/2022 ¹⁵	01/09/2022 ¹⁶	
Comirnaty original strain + omicron ba4/5 (adapted, bivalent)	09/11/2022 ¹⁷	12/09/2022 ¹⁸	
Spikevax original strain (monovalent)	31/03/2021 ¹⁹	06/01/2021 ²⁰	
Spikevax original strain + omicron ba1 (adapted, bivalent)	15/08/2022	01/09/2022	
Spikevax original strain + omicron ba4/5 (adapted, bivalent)	21/02/2023 ²¹	19/10/2022 ²²	

Table 8.6.1.1 provides an operational definition of COVID-19 exposure status.

	Phase II C3-002 – Study Protocol	
	Author(s): [name], [name], [name]	Version: v2.1
	Dissemination level: Public	

Table 8.6.1.1 Operational definition of exposure status

Exposure group name(s)	Details	Washout window	Assessment Window	Care Setting ¹	Code Type	Applied to study populations:	Incident with respect to...
Covid-19 vaccinated: 1 dose only	Exactly 1 Comirnaty/Spikevax vaccination record	Anytime in a patient's history	[-anytime, ID]	OP	RxNorm	Source population	COVID-19 vaccination
Covid-19 vaccinated: Completed primary vaccination course	Exactly 2 vaccination records, with the latest being Comirnaty/Spikevax	21 days	[-21, ID]				n/a
Covid-19 vaccinated: 3 rd dose	Exactly 3 vaccination records, with the 3 rd dose being either monovalent or any of the adapted, bivalent Comirnaty/Spikevax vaccines	90 days	[-90, ID]				n/a
Covid-19 vaccinated: 4 th dose, monovalent or adapted/bivalent	Exactly 4 vaccination records, with the latest being Comirnaty/Spikevax	90days	[-90, ID]				n/a

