Large-scale propensity scores (PS) will be computed to estimate the probability of receiving a 4th vaccine dose. Covariates to be included in the large-scale PS will be selected from co-medications and comorbidities recorded prior to cohort-specific index dates. Among those, covariates with a prevalence below 0.5% in the study population will be omitted. Logistic regression with LASSO regularization will then be used for variable selection. The list of selected covariates will be manually screened by 2 epidemiologists/clinical domain experts to exclude potential instrumental variables.

The same procedure will be conducted in the calendar week after, with previously non-boostered people being allowed to be included in the booster cohort once they change exposure status. Non-boostered people can only be matched once to a booster counterpart during the whole study. With matching, non-boostered counterparts will be assigned the date of when the booster counterpart received their 4th vaccine dose as their “final” index date (index date for the matched pair).

All booster and matched non-boostered people from sequential weekly matching will be combined into the booster and non-boostered cohort for subsequent analyses. The study inclusion and sequential matching process is illustrated in [Figure 8.8.3.1](#) below.

[figure not shown]

	Phase II C3-002 – Study Protocol	
	Author(s): [name], [name], [name]	Version: v2.1
	Dissemination level: Public	

Figure 8.8.3.1 Study inclusion and sequential matching process

	Phase II C3-002 – Study Protocol	
	Author(s): [name], [name], [name]	Version: v2.1
		Dissemination level: Public

Follow-up

In the matched cohorts, people will be followed up from their index date until the earliest of

- End of their observation (i.e. date of data extraction, death)
- 2nd booster vaccination for unvaccinated group, 3rd booster for vaccinated group etc.
- COVID-19 related hospitalization or death, with outcome date being defined as the date of first COVID-19 diagnosis/positive test related to hospitalization or death.

Follow-up will be censored for the matched pair if one counterpart is censored, but not if one counterpart experiences the outcome.

Outcomes

The outcomes are defined in detail in section 8.6.2.

COVID-19 related hospitalization will be assessed for SIDIAP and IPCI. COVID-19 related death will be assessed for CPRD, IPCI and SIDIAP.

Statistical Analyses

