Objective 1: Vaccine effectiveness

Cox proportions hazard models will be used to calculate hazard ratios (HR) for the outcomes of COVID-19 related hospitalisation and COVID-19 related death.

Negative control outcomes will be used as an additional measure to measure any potential residual confounding. NCO are outcomes not causally associated with the exposure of interest²⁶, here COVID-19 vaccination. However, their association with vaccination is ideally impacted by the same type of unmeasured confounding, e.g. healthcare-seeking behavior, as the vaccination-outcome association²⁷. In the scenario of potential unmeasured confounding being detected by NCO, empirical calibration²⁵ for HR might be considered to minimise bias.

Vaccine effectiveness will be calculated as $1 - HR$. Kaplan Meier plots and/or cumulative incidence plots will be used to illustrate survival analyses.

The proportional hazard assumption will be tested visual investigation of log(-log) plots. In the scenario of substantial violation of the proportional hazard assumptions, alternative models/model adaptations will be used.

Objective 2: Waning of vaccine effectiveness

Hazard ratios will be calculated for subsequent time windows after index date, i.e. in bi-weekly intervals. Monthly intervals will be used in case of small event counts to increase sample size and power if needed. Vaccine effectiveness will be calculated as $1 - HR$.

Kaplan Meier plots and/or cumulative incidence plots will be used to illustrate survival analyses.

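### In IPCI and CPRD, Objective 2's window hazard ratios mix waning with a drift in product and index date, of a direction and size that the protocol does not determine

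*Protocol*

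**What the plan says.** Table 7.1 of the Protocol places waning (Objective 2) under the primary research question. Section 8.8.3 fixes the estimator: "Hazard ratios will be calculated for subsequent time windows after index date, i.e. in bi-weekly intervals", with VE taken as 1 - HR. The only fallback is window width: "Monthly intervals will be used in case of small event counts to increase sample size and power if needed".

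The same section fixes the population in each window. Matching runs week by week from the start of the 4th-dose programme, and then "All booster and matched non-boostered people from sequential weekly matching will be combined into the booster and non-boostered cohort for subsequent analyses". On exit from follow-up: "Follow-up will be censored for the matched pair if one counterpart is censored, but not if one counterpart experiences the outcome". Follow-up also ends at data extraction, which Table 8.2.1 gives under "Data lock for the last update" as 12/2022 (IPCI), 01/2023 (CPRD GOLD) and 06/2022 (SIDIAP).

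On the start, section 8.3 says: "Analyses will therefore start at the time when vaccine booster programs offering the 4th vaccine dose were rolled out in each country". The abstract gives 01/08/2022.

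On product, section 8.2 says: "Information on vaccine products (i.e. monovalent/bivalent booster) are not reliably recorded in the databases, but only the vaccine brand". Section 8.8.6 stratifies by brand and by age at 65 years, adds an immunocompromised subgroup, and plans no sensitivity analyses.

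**The concern.** Objective 2 asks whether protection from a given 4th dose declines with time since that dose. A series of window HRs answers this only if the windows describe comparable pairs. Here they do not: a pair indexed late runs into the data lock early, so the later windows are filled only by the earlier-indexed pairs. In IPCI and CPRD this drift crosses a change of vaccine, because the index period begins before the first adapted products were approved and ends well after. It also tends to leave the groups invited first in the later windows.

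Matching balances the two arms within a pair. It does not keep the product, or groups with a different VE, in constant proportion from one window to the next. A difference between windows is then a mixture of waning and changing composition, and nothing in the stated analysis separates them. The risk is a report on a primary objective that reads one as the other, in either direction.

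**Working it through.** The Protocol states no waning figure, event count or test, so there is nothing to reproduce. The check uses its dates and its censoring rules.

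**1. How far a post-approval dose can reach.** Inputs: approval dates from Table 8.6.1.1 (marketing approval dates), locks from Table 8.2.1 (month only, so first and last day of the month are both used), start 01/08/2022 from the abstract. Reach = lock - approval date; maximum follow-up = lock - 01/08/2022.

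| Database, brand | First adapted approval | Lock | Maximum follow-up (days) | Reach of a post-approval dose (days) |
|---|---|---|---|---|
| IPCI, both brands | 01/09/2022 | 01/12 to 31/12/2022 | 122-152 | 91-121 |
| CPRD, Comirnaty | 02/09/2022 | 01/01 to 31/01/2023 | 153-183 | 121-151 |
| CPRD, Spikevax | 15/08/2022 | 01/01 to 31/01/2023 | 153-183 | 139-169 |

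Beyond the reach, every 4th dose in the window predates approval and is monovalent. With month-end locks and 14-day windows this covers windows 10-11 of 11 in IPCI, windows 12-13 plus a one-day window 14 for CPRD Comirnaty, and only the one-day window 14 for CPRD Spikevax. With locks on the first of the month it covers windows 8-9 of 9, 10-11 of 11, and 11 of 11.

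**2. The drift before that point.** Let F(d) be the share of 4th doses given by day d after 01/08/2022, A the days before approval and L the days to lock. If pairs leave for other reasons at the same rate whatever their index date, the pre-approval share at time t since dose is s(t) = F(A) / F(L - t), capped at 1. It cannot fall as t grows, whatever the uptake. Unequal next-dose censoring would change the path but not the end point.

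IPCI, lock 31/12/2022, A = 31, L = 152, uniform uptake (assumed):
- window 1 (mean day 6.5): 31/145.5 = 21%
- window 6 (mean day 76.5): 31/75.5 = 41%
- window 8 (mean day 104.5): 31/47.5 = 65%
- window 9: 90%; windows 10-11: 100%

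With uptake peaking around 10 October (also assumed) the shares in windows 1, 6, 8, 9 and 10-11 are 3%, 5%, 21%, 67% and 100%.

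**3. What this does to VE when neither product wanes.** HR in window w = s_w × HR_mono + (1 - s_w) × HR_biv. The bivalent HR is set at 1 - 0.678 = 0.322, using the abstract's 67.8% purely as an illustrative constant. Post-approval doses are treated as bivalent. Monovalent VE is not in the documents and is varied. Example, monovalent VE 40%, window 1, uniform uptake: 0.213 × 0.60 + 0.787 × 0.322 = 0.381, so VE is 62%.

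| Assumed monovalent VE | VE in first / middle / last window (IPCI, uniform uptake) |
|---|---|
| 40% | 62 / 56 / 40% |
| 50% | 64 / 60 / 50% |
| 60% | 66 / 65 / 60% |
| 67.8% (equal) | 68 / 68 / 68% |
| 75% | 69 / 71 / 75% |

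With the October peak and monovalent VE 40%, the series is 67 / 66 / 40%, and nearly all of the fall comes in the last 3-4 windows.

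**4. How much data sits in the tail.** For IPCI under uniform uptake with no other censoring, windows 10-11 start at day 126 and hold (152 - 126)² / 152² = 676/23,104, about 3% of pair-time. Across the assumed uptake and censoring patterns the share is about 0.1% to 6% in IPCI and CPRD Comirnaty (month-end locks).

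**5. After the change.** Split at approval, the same no-waning inputs give two flat series and no spurious fall, provided post-approval doses are all of one product.

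**The case against.** Several points on the other side are sound.

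- The wholly monovalent windows are only the last few and nearly empty, so an end-to-end comparison such as 62% against 40% sets a well-filled window against one with very few events. The monthly fallback makes such a window less likely to be read alone, though it does not stop the drift.
- SIDIAP, the largest database, locks before every adapted-vaccine approval and before 01/08/2022. No product change can occur there on the stated cut.
- The 67.8% concerns a BA4/5 dose and hospitalisation. CPRD contributes only COVID-19 death, and UK BA4/5 approvals came on 09/11/2022 (Comirnaty) and 21/02/2023 (Spikevax), the latter after the CPRD lock. The figure cannot size the effect in CPRD.
- Cohorts 3 and 4 would separate monovalent from bivalent 4th doses where product is reliably recorded. Section 8.2 says it is not in these databases, so this safeguard does not operate here. Age stratification and the immunocompromised subgroup address the early-invited groups only in part.

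A reader might infer that the plan will overstate waning, or that it has an inflated false-positive rate for waning. The documents support neither. The first needs bivalent VE above monovalent VE, and no monovalent VE is given; at 75% the drift would hide real waning. The second needs a test, and Table 7.1 lists the hypothesis as not applicable.

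What remains is the mechanism. The Protocol itself fixes the estimator, the pooling, the strata and the absence of sensitivity analyses, so this is not a detail left to a later analysis plan.

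**Conclusion.** The point holds for IPCI and CPRD. On the Protocol's own dates and rules, the index-date and product mix changes across the Objective 2 windows, and becomes wholly monovalent beyond about day 91-121 (IPCI), 121-151 (CPRD Comirnaty) and 139-169 (CPRD Spikevax). A change in VE between windows therefore cannot be attributed to waning alone.

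The effect on the estimates ranges from none (equal VE) to large, in either direction, and depends on monovalent VE and weekly uptake, which the documents do not give. It bears on COVID-19 death in both databases, and on hospitalisation only if IPCI supplies it, on which the Protocol's sections disagree.

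The day ranges assume a start on 01/08/2022. If the 4th dose became available earlier, as the wording of 8.8.3 would allow, the monovalent-only tail is longer. A later data cut would move the tail to later windows without removing it.

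**What to change.** In section 8.8.3, Objective 2, add window HRs that are:

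- restricted to pairs whose index date allows potential follow-up, up to the data lock, through the last window reported; and
- shown separately for pairs indexed before, and on or after, the first adapted-vaccine approval date for that brand and country in the marketing approval table (Table 8.6.1.1).

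State that a fall in VE will be attributed to waning only if it also appears in these series. Keep the all-pairs series, and give the index-date range and number of pairs in each window. No product record is needed, because doses given before approval can only be monovalent.

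The cost is protocol wording and a filter on dates already held, with wider intervals and a shorter span after approval. For example, a 12-week (84-day) post-approval series in IPCI admits index dates 01/09 to 08/10/2022 with a 31/12/2022 lock, and only 01/09 to 08/09/2022 with a 01/12/2022 lock.

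Two limits should be stated. Pairs still leave when either member has the next dose, so the set is not fixed; only the lock-driven drift is removed. And the post-approval stratum may still mix monovalent and different adapted products.
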